1. PURPOSE OF THE STUDY AND BACKGROUND

1.1. Purpose of the study

This study is intended to determine if treatment with the oral agent pioglitazone (also called Actos, a drug approved to treat diabetes) can decrease the number of new squamous cell cancers in people who have a high risk of developing skin cancer. This patient population includes, but is not limited to those with immunosuppression secondary to organ transplantation.

Specifically, the purposes of this pilot study are to collect preliminary data in order to plan for a larger study, the objective of which will be to assess whether pioglitazone will:

- Decrease the number of new skin cancers patients develop while taking the drug compared to their stable baseline
- Determine if skin cancer formation reoccurs when stopping drug
- Determine if the study drug affects the phenotype of the skin cancers occurring while on treatment (i.e., well differentiated vs. poorly differentiated tumors)
- Change the expression of markers influenced by PPAR γ or AKR1C3 (apoptosis, proliferation) in tumors removed from treated patients.

1.2. Background

Squamous cell carcinoma (SCC) is the second most common form of skin cancer, with a steadily increasing annual incidence of over 250,000 cases in the United States(Miller *et al.*, 2010; Schmults *et al.*, 2013). The mortality rate of these cancers remains low (~1 %), however in certain populations such as organ transplant recipients, rates of metastasis and mortality are considerably higher(Mullen *et al.*, 2006). When patients develop metastatic disease, up to 50 % will have a recurrence with a mortality rate of up to 85 % (Goh *et al.*, 2010). Beyond mortality and high morbidity, treating non-melanoma skin cancers is costly, accounting for 4.5 % of all Medicare cancer costs, a figure that increased 41 % between 1992 and 1995(Rogers *et al.*, 2010). Clearly, therapies that can prevent or stop the progression of SCC are sorely needed. Recent work demonstrated that selective inhibition of prostaglandin E synthesis using Celebrex resulted in a 40 – 50% decrease in squamous cell cancers over a 6 month period(Elmets *et al.*, 2010). However, the utility of Celebrex and other NSAIDs is decreased because of the significantly increased risk of heart attacks(Schmults *et al.*, 2013).

[figure not shown]

Figure 1, above. PGD₂ and 15d-PGJ₂ attenuated SCC cell proliferation in a PPAR_γ-dependent manner. (a) SCC cells were treated with the indicated concentration of PGD₂, 15d-PGJ₂, 9α,11β-PGF₂ or DMSO for 24 hours followed by cell proliferation assessment by Click-iT assay. Data presented is the average of 3 experiments (±SEM), *P<0.005, **P=0.012. To study the involvement of PPAR_γ activation in the anti-proliferative effects mediated by 15d-PGJ₂ and by its precursor PGD₂, SCC cells were treated with 1.5μM 15d-PGJ₂ (b) or 7μM PGD₂ (c) in the presence of the indicated concentration of the PPAR_γ specific inhibitor GW9662 (GW). Cell proliferation was assessed by Click-iT assay. n=3 *P<0.05. (d) The effects of Pioglitazone on SCC proliferation. Each SCC cell line was treated for 24h as indicated and cell proliferation was assessed by Click-iT assay.(n=3)

Aldo-Keto Reductase 1C3 (AKR1C3) is another prostaglandin-synthesizing enzyme that could be a target for SCC prevention(Matsuura *et al.*, 1998). AKR1C3 belongs to a large superfamily of NAD(P)(H)-dependent AKR enzymes which metabolize various substrates including prostaglandins and sex hormones (Jez and Penning, 2001). In humans, the AKR1C subfamily consists of 4 enzymes termed AKR1C1, AKR1C2, AKR1C3 and AKR1C4 which despite their extensive structural overlap, exhibit different substrate binding preferences (Penning *et al.*, 2000). Among these enzymes, AKR1C3 expression has been associated with cancer risk.

AKR1C3 is overexpressed in various cancers originating from non-steroidogenic tissues such as kidney (Azzarello *et al.*, 2009), central nervous system (Park *et al.*, 2010), pancreas, gastrointestinal tract and lung (Chang *et al.*, 2013; Miller *et al.*, 2012). AKR1C3 can activate carcinogens (Lan *et al.*, 2004), modulate oxidative stress (Birtwistle *et al.*, 2009), and its polymorphisms are associated with risk for childhood leukemia (Liu *et al.*, 2008) and bladder cancer (Figueroa *et al.*, 2008). Collectively, these observations suggest a tumor promoting function for AKR1C3 (Azzarello *et al.*, 2009; Miller *et al.*, 2012). Unlike other AKR1C members, AKR1C3 can also synthesize PGF_{2α} from PGH₂, an arachidonic acid derivative synthesized by cyclooxygenase (Komoto *et al.*, 2006). Its role in prostaglandin metabolism also includes the conversion of PGD₂, a pro-inflammatory lipid mediator, to 9α,11β-PGF₂ (Byrns *et al.*, 2010; Komoto *et al.*, 2006; Matsuura *et al.*, 1998). Thus, via its involvement in PG metabolism and its downstream effects on PPAR_γ, AKR1C3 may regulate biological and pathological responses in hormone-independent tissues.

Our recent work investigated AKR1C3 expression in human non-melanoma skin cancers, revealing overexpression in 7 human squamous cell carcinomas (SCC) examined. Effects of AKR1C3 expression were then evaluated using 3 SCC cell lines (Fig. 1). AKR1C3 was detected in all SCC cell lines and its expression was upregulated in response to its substrate, PGD₂. Treatment of the SCCs with PGD₂ and its dehydration metabolite, 15d-PGJ₂,decreased SCC proliferation, indicating that the PPAR_γ receptor was the key effector of this profound inhibitory response. **SCC treatment with the PPAR_γ**

agonist pioglitazone was then tested, showing a profound capacity to inhibit SCC proliferation, using concentrations achieved in patients on drug treatment (50 – 100 μ M)(Christensen *et al.*, 2005). This work suggests that AKR1C3 over-expression within the tumor microenvironment may protect SCC cells from the anti-proliferative effects of PGD₂ and that PPAR γ agonists such as pioglitazone may be a useful treatment adjunct for those at high risk of SCC. There are no currently available approved selective inhibitors of AKR1C3. However, Pioglitazone is a currently approved oral treatment for diabetes that can be safely administered to non-diabetics(Bell *et al.*, 2012). We propose to learn in this clinical trial if its use can be helpful in patients who develop multiple SCCs each year. The protocol outlined here is intended to examine this possibility as well as address the mechanisms by which it exerts its effects.

2. STUDY DESIGN

2.1. Overview

This is a single center open label feasibility pilot project based at the University of Rochester. Patients followed in the University of Rochester Dermatology Clinic who have had between 2 to 6 squamous cell cancers treated in the past year, without contraindication for the use of Pioglitazone, and are on a stable drug treatment regimen will be offered participation. The study has a cross-over design, so patients will be enrolled and randomized in one arm of two treatment protocols: 1) six months of usual care while documenting and characterizing any new tumors that occur followed by 6 months of Pioglitazone treatment plus usual care for the next 6 months or 2) six months of Pioglitazone treatment followed by 6 months off treatment receiving usual care (see protocol diagram, Section 5, below). The second group will offer the opportunity to assess whether there is any persistent beneficial effect after pioglitazone treatment ends, while tumors from the first group that occur during the initial 6 months of usual care will be characterized by study parameters for comparison to tumors arising while on treatment. At the end of the one year treatment period, the number of new tumors that patients develop while taking Pioglitazone will be counted and compared with the number that patients developed during the 6 month period they were not receiving treatment as well as the numbers that occurred during the 6 months after treatment (washout effect). This information will be used as the basis for a larger multicenter study.

[figure not shown]

Fig 2. Schematic for the Proposed Study (study visit day are +/- 7 or 14 days)

2.2. Rationale for Study Design

An open label study with a crossover design was selected because this is a feasibility pilot project funded by the Department of Dermatology, and we require a study design that can yield useful statistical information for sample size for a subsequent multi-center trial with the number of subjects we are likely able to recruit here at Rochester. We calculate that 40 patients will be needed to provide the sample size required to determine a statistically significant drug effect for a larger study. We also expect that it may not be possible to identify and enroll more high risk patients at Rochester in a reasonable period of time given the incidence of multiple SCC and the eligibility criteria. It is possible this design may not give a long enough period of time on drug to substantially decrease the onset of new tumors, however we believe it will be sufficient since 2 other drugs that affect the frequency of SCC in susceptible patients do produce substantial effects in this time frame (Celebrex, Soriatane)(Elmets *et al.*, 2010; Kadakia *et al.*, 2012). A one year long study will permit completion of a feasibility pilot in a reasonable period to allow a larger, definitive study to be done. We hypothesize that Pioglitazone will have the capacity to reduce incidence of SCC by >50%, as >90% decrease in growth is seen in tissue culture of human SCC using levels of pioglitazone available in human serum (see preliminary data, above). This is also the effect size seen with Celebrex treatment, a drug that can also selectively modulate prostaglandin synthesis.

We have chosen tumor incidence as the primary outcome measure. Because patients with high tumor risk develop new tumors at a variable pace, some subjects may not have any new tumors during the period of the study. However, in aggregate we feel that a tumor endpoint is the best choice. This decision was made because of our recent experience studying the effects of Celebrex on skin cancer incidence. That study assessed pre-skin cancers (actinic keratoses) as the primary endpoint(Elmets *et al.*, 2010). However, when data was analyzed, it was found there was no significant change in precursor lesions, only in actual tumor numbers. Thus, we have elected to focus on a high risk population that will have high numbers of new tumors. These patients are also the target group that could derive the most benefit from treatment.

This study will also assess secondary endpoints. First, we will examine whether the ratio of well-differentiated to poorly differentiated SCC is influenced while subjects are on treatment. This endpoint is included because it is unknown whether there may be more signaling mediated by PPAR γ in one tumor morphology vs. another. Second, we will determine whether patients on treatment might have different numbers of “borderline” lesions biopsied; precancerous lesions are often suspicious enough to biopsy. It may be that there will be fewer lesions in this category, as well as fewer squamous cell cancers. Third, we will test tumors that are excised after they are processed for routine diagnostic pathology to see if markers of proliferation or apoptosis that are influenced by PPAR γ activity or the presence of AKR1C3 are altered. These endpoints would support the idea that any changes produced in tumor incidence while patients are on study drug are related to the mechanistic effect on PPAR γ that is proposed.

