5.1. Efficacy Assessments

Administration of Pioglitazone to prevent/decrease the aggressive phenotype of skin cancer is experimental. NB- obtaining biopsy of lesions suspected of skin cancer is NOT experimental; it is required for usual patient care in these high risk patients. In order to know whether Pioglitazone is efficacious for preventing SCC in high risk individuals, we will count the number of skin tumors documented by biopsy/treatment that occur in our subjects before, during, or after Pioglitazone treatment. This assessment will take into account compliance, as described below. The tumor counts will be best interpreted in aggregate for the whole sample group, since there is variability in the frequency with which new tumors appear based on the predisposing condition. Since Pioglitazone has been on the market for some time without observation of a negative impact on skin or wound healing, the study focus will be determining if numbers of tumors decrease and whether their phenotype changes. The physician reading the pathology of the skin biopsies will be responsible for identifying the number of tumors that occur –i.e., some lesions thought to be tumors and therefore biopsied in clinical practice turn out to be hypertrophic actinic keratosis (not tumors). These would not be counted as skin cancers, since they are precancerous lesions.

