13. DATA ANALYSIS AND MONITORING

13.1. Sample Size Determination

[figure not shown]
This pilot study will be designed as a 2-by-2 crossover trial. We refer to Section 2.2 for a justification of the study design. Patients will be enrolled and randomized in one arm of two treatment protocols. Each protocol will include two treatments administered during two consecutive time periods:

- Treatment arm # 1: Patients enrolled in the first arm will first receive six months of usual care (*Period 1*); next, they will be treated with Pioglitazone combined with usual care for the next 6 months (*Period 2*). Patients will take study drug until they come to their final “on Treatment” visit, which will occur 168 days +/- 14 days of their “on Treatment” date.
- Treatment arm # 2: Patients enrolled in the second arm will first receive six months of Pioglitazone treatment combined with usual care (*Period 1*); next, they will receive usual care alone during the following 6 months (*Period 2*). Patients will take study drug until they come to their final “on Treatment” visit, which will occur 168 days +/- 14 days of their “on Treatment” date.

A flow diagram describing the study design is presented in Section 2.

The primary endpoint will be the total number of skin tumors counted during each treatment period. Based on clinical evidence, we expect the total number of skin tumors to range between 0 and 3 per patient and per treatment period (or 0 to 6 per patient per year) and to average around 1.5. We would consider Pioglitazone to be clinically effective if it reduces tumor counts by 50% (that is, reduce the average number of tumors from 1.5 to 0.75 per patient and per treatment period). Previous work by this investigator has shown that such reductions in tumor numbers can occur when prostaglandin metabolism is affected by drug treatment (Elmets *et al.*, 2010).

A two-sided *t*-test achieves 96% power to detect a reduction in the number of skin tumors due to Pioglitazone when the total sample size of a 2-by-2 crossover design is 40 (20 patients per group). The calculations assumed that the actual mean difference is 0.75 (corresponding to a 50% reduction in the mean number of skin tumors due to treatment), the square root of the within mean square error is 1, and the significance level is 5%. The figure below displays the power of the study as a function of the sample size (N) for three values of the square root of the within mean square error (SW).

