13.2. Planned Statistical Analysis

The main objective of the statistical analysis will be to estimate the effect of Pioglitazone on the occurrence of skin tumors when used in combination with usual care compared to usual care alone. The primary endpoint will be the total number of skin tumors counted during each treatment period. We will have two observations per patient, one for each treatment period of the 2-by-2 cross-over design (either baseline to 6 months, or 6 months to 12 months post-baseline). We will first compute the empirical mean (and its standard error), standard deviation and median for the number of skin tumors within each treatment arm and each treatment period. We will also construct histograms for tumor counts. We expect tumor counts to range between 0 and 6 per six months, such that parametric mixed analysis of variance (ANOVA) may not be the most appropriate approach to assess treatment effects. As an alternative, we will describe the number of skin tumors using log-linear Poisson regression models with random effects. The developed models will include treatment arm, period, and their interaction as covariates while adjusting for potential intra-subject dependencies (or between subject variation) using random intercepts. We will use this model to investigate the presence of washout effect (secondary aim).

In additional, exploratory analyses, we will assess if the phenotype of skin tumors changes during treatment with Pioglitazone. We will also determine if Pioglitazone changes the expression of markers influenced by PPAR γ or AKR1C3 (apoptosis, proliferation) in tumors removed from treated patients. We will have an apoptosis and a proliferation score for every skin tumor that arises, both treated as continuous variables. The analyses will be conducted using mixed ANOVA modeling the apoptosis and the proliferation scores of each tumor as a function of treatment arm,

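### The well- to poorly-differentiated ratio can indicate a morphology-selective effect but cannot by itself show whether poorly differentiated SCCs became fewer, unchanged or more frequent; counts of each class should be added

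*Combined protocol and SAP*

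**What the plan says.** Section 1.1 lists the objective: "Determine if the study drug affects the phenotype of the skin cancers occurring while on treatment". It explains phenotype as well versus poorly differentiated tumors. Section 2.2 turns this into the first secondary endpoint: "we will examine whether the ratio of well-differentiated to poorly differentiated SCC is influenced while subjects are on treatment". The reason follows at once: "This endpoint is included because it is unknown whether there may be more signaling mediated by PPAR" γ in one morphology than in another.

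Section 5.1 describes the aim in terms of aggressive disease: "Administration of Pioglitazone to prevent/decrease the aggressive phenotype of skin cancer is experimental".

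Section 13.2 treats the question as exploratory: "In additional, exploratory analyses, we will assess if the phenotype of skin tumors changes during treatment with Pioglitazone". It names no measure, model or denominator for this, and it does not mention the ratio. The only count that the plan analyzes per patient and period is the total: "The primary endpoint will be the total number of skin tumors counted during each treatment period". No section plans counts or rates by differentiation class.

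**The concern.** A ratio among tumors that arise is conditional on an event after randomization that the drug is expected to alter. Section 13.1 takes as clinically effective a halving of the tumor count. If such an effect falls unevenly on the two classes, the ratio moves; if it falls evenly, the ratio stays put. In neither case does the ratio say how many poorly differentiated tumors patients had.

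That number matters because section 5.1 speaks of preventing or decreasing the aggressive phenotype. A fall in the ratio could be read as a shift toward aggressive disease when poorly differentiated tumors had not increased. A stable ratio could hide a real reduction in them. The pilot is meant to inform a larger study, so either misreading could carry forward.

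**Working it through.** **Inputs from the documents.** Section 13.1 gives 40 patients in a 2-by-2 crossover, each with one period on drug and one off, and the target effect: "reduce the average number of tumors from 1.5 to 0.75 per patient and per treatment period". The plan states no figure for the phenotype endpoint, so there is none to reproduce; its 96% power concerns the total count only.

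**Assumptions.** The documents give no poorly differentiated share. I take 20% for the example and 5% to 30% as the range. All counted tumors are treated as SCCs in one of two grades, and all 40 patients complete both periods.

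**Expected totals.** Off drug: 40 × 1.5 = 60. On drug at the target effect: 40 × 0.75 = 30.

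**Example at a 20% poor share.** Off drug: poor 0.20 × 60 = 12, well 48.

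| Scenario | Well:poor | Ratio | Well per patient-period | Poor per patient-period |
|---|---|---|---|---|
| Off drug | 48:12 | 4.0 | 48/40 = 1.20 | 12/40 = 0.30 |
| A. On drug, only well-differentiated tumors prevented | 18:12 | 1.5 | 18/40 = 0.45 | 12/40 = 0.30 |
| B. On drug, poorly differentiated tumors doubled | 36:24 | 1.5 | 36/40 = 0.90 | 24/40 = 0.60 |
| C. On drug, both classes halved | 24:6 | 4.0 | 24/40 = 0.60 | 6/40 = 0.15 |

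A and B share a ratio although the poor rate is unchanged in one and doubled in the other. C has the usual-care ratio although the poor rate is halved.

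**Range for scenario A** (total halved, poor count unchanged):

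- 5%: 57:3 = 19 becomes 27:3 = 9
- 10%: 54:6 = 9 becomes 24:6 = 4
- 20%: 48:12 = 4 becomes 18:12 = 1.5
- 30%: 42:18 = 2.33 becomes 12:18 = 0.67

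The direction is the same throughout; the size depends on the assumed share.

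**What the ratio does measure.** The on-drug ratio divided by the off-drug ratio equals the well-class rate ratio divided by the poor-class rate ratio. In A: 1.5/4.0 = 0.375, and (18/48)/(12/12) = 0.375. In C: 4.0/4.0 = 1, and (24/48)/(6/12) = 1. It measures relative selectivity and leaves the level of each class open.

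**Precision of the poor-class rate.** For a true halving at a 20% share (12 versus 6), the standard error of the log rate ratio is √(1/12 + 1/6) = 0.5. The 95% interval factor is exp(1.96 × 0.5) = 2.66, so a rate ratio of 0.50 has an interval of about 0.19 to 1.33. An exact conditional test of two Poisson counts has power of about 2%, 9%, 22% and 33% at poor shares of 5%, 10%, 20% and 30%.

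**The case against.** The strongest reply is that the ratio fits its stated purpose. Section 2.2 includes it to learn whether the drug acts more on one morphology, and for that question uneven prevention is the signal. The move from 4.0 to 1.5 in scenario A correctly reports selectivity. This stands: a reader might infer that the ratio is invalid or gives the wrong sign, and for its own rationale it does neither. The gap concerns the number of aggressive tumors, which section 5.1 raises and no planned measure addresses.

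A second reply is that the ratio will be read beside the total. Thirty tumors at 1.5 can only be 18 + 12, and sixty only 36 + 24, so the total separates A from B. This stands in part. It requires every counted tumor to be an SCC in one of two grades. The endpoint is worded as skin tumors, and the plan does not say so.

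Two stronger readings are tempting.

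- A reader might infer that the ratio is undefined for many patients and discards the randomized comparison. Under independent Poisson counts, exp(−1.5) = 22% of off-drug and exp(−0.75) = 47% of on-drug periods have no tumor, and 0.777 × 0.528 = 41% of patients (about 16 of 40) have tumors in both. That matters only for a ratio formed within patients. The plan never specifies one, and section 5.1 says tumor counts are best interpreted over the whole group. Pooled ratios such as those above are defined.
- A reader might infer that class rates would reveal whether tumors changed phenotype. They would not. The move from 48:12 to 18:12 fits prevention of 30 well-differentiated tumors. It equally fits a halving of both classes to 24:6 followed by six tumors shifting from well to poor.

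Finally, the analysis is exploratory in section 13.2, the study is a pilot, and power for the poor class is low. All true, and this limits the priority.

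**Conclusion.** The point holds in a limited form. The ratio can indicate a morphology-selective effect, but alone it cannot show whether poorly differentiated tumors fell, stayed or rose. At an assumed 20% share, one ratio (1.5) covers both an unchanged and a doubled poor rate, and another (4.0) covers both usual care and a halved poor rate.

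The sizes rest on the rates in section 13.1, the assumed share and deliberately simple scenarios. The loss of level information is a property of any ratio and does not depend on the share. The endpoint is secondary in section 2.2 and exploratory in section 13.2, so the primary analysis is untouched. Low priority.

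**What to change.** In sections 2.2 and 13.2, add two outcomes: the number of well-differentiated and the number of poorly differentiated SCCs per patient per period, with zero recorded for tumor-free periods. Analyze each with the Poisson random-intercept crossover model already planned for the total count, or with a simpler Poisson or GEE fit if counts are too sparse. Report estimates with confidence intervals.

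Keep the ratio as a descriptive, aggregate measure of selectivity, and state that it is conditional on tumors that occurred. Attach the same caveat to the apoptosis and proliferation scores, which also exist only for tumors that arise. State that class rates describe the burden of each class and do not distinguish a change in tumor phenotype from selective prevention.

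The cost is a few sentences and two model fits. No new data are needed, since the ratio already requires each SCC to be graded. The downside is wide intervals for the poorly differentiated class, as the precision figures above show.
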